5.6.3 Prohibited Concomitant Therapy

Any medication administered for the treatment of any psychiatric or neurologic disorder or any other known CNS active drugs, including herbal, over-the-counter, and homeopathic medications, MAOIs, other antidepressants, antipsychotics, stimulants and mood stabilizers are prohibited during this study (See Appendix A, Concomitant Medication Exclusion List). Use of Zaleplon, zolpidem, zopiclone or lorazepam for more than the permitted days (see above) or beginning a new regimen of hormonal contraception may lead to excluding the participant from the study.

6 Study Procedures

6.1 Phase I Visit 1 (Screening)

Table 2 describes all study assessments. Table 3 describes a schedule of events. The first visit is a screening visit. Informed consent and assent will be completed. A physical exam, vital signs, urine drug screen, and urine pregnancy test (if applicable) will be completed. Baseline assessments may be completed at this time as well in the interest of decreasing patient burden related to study procedures (see Table 3).

Once eligibility criteria are met and interest in the MRI/MRS is indicated, the subject will report to the University of Minnesota Center for Magnetic Resonance Imaging for the 3 and 7 Tesla MRI Scans. This procedure needs to be completed prior to the Baseline Visit.

6.2 Phase I Visit 2 (Baseline)

Assessments will be completed (see Table 3), TMS neurophysiology measures are collected, and the participant is stratified as described previously based on ICF (**ICF-15 % MEP amp**)

biomarker status. The participant is randomized to 1 Hz or 10 Hz rTMS. Based on participant preference, the baseline visit can be scheduled on a Monday to facilitate the initiation of investigational rTMS treatment (1 Hz or 10 Hz based on randomization). Otherwise, the participant will be scheduled to initiate the first investigational rTMS treatment day as appropriate based on the patient’s schedule and staffing availability.

6.3 Phase I Daily Treatment Visits

On each treatment visit 1 Hz or 10 Hz rTMS will be delivered as described previously. Additionally, for the first week of Phase I treatment, a pre-treatment checklist will be completed by 2 members of study staff prior to initiating treatment to ensure treatments are performed properly and accurately. The 2nd member of study staff may assist telephonically if necessary. Participants will undergo weekly depression severity measures and TMS neurophysiological measures (see Table 3).

Table 2. Description of Assessments

| Assessment | Description |
|--|--|
| Abnormal Involuntary Movement Scale (AIMS) | Collected at the screening visit and at weekly treatment visits, posttreatment, and 6-month follow up visit. This assessment is to screen and monitor twitching, trembling, and dyskinesias. |
| Antidepressant Treatment History Form (ATHF) | Collected at baseline to systematically document prior psychotropic medication exposure and for quantification of treatment resistance (number of failed antidepressant trials with an adequate dose and duration). |
| Adverse events | Participants will be evaluated for adverse events at each visit. Serious adverse events (SAEs) will be reported as they occur to the Mayo Clinic IRB and USA FDA (as per regulations). Systematic data collection focused on adverse events will include the Pediatric Adverse Event Rating Scale and Physical Symptom Checklist. These rating scales will be administered at baseline, weekly (during all rTMS, cTBS, and iTBS treatment weeks), at the 6 month follow up visit, and at study exit. |
| Auditory thresholds | Participants will undergo audiometry testing at baseline and upon completion of 6 week rTMS (1 Hz or 10 Hz) and once again (if applicable) after the two week open extension trial (of either cTBS or iTBS). |
| Beck Depression Inventory-II | This is a validated, 21-item, self-report measure with a range of 0-63. Collected at baseline, weekly during treatment, posttreatment, and 6 month follow up visit. |
| CDRS-R – Childhood Depression Rating Scale – Revised | This is a validated, 17-item, clinical rating tool to assess severity of depression. Parents provide input into 14 of the items. Total possible scores range from 17 to 113. Collected at baseline, weekly during treatment, posttreatment, and 6 month follow up visit. |

| Assessment | Description |
|--|--|
| CGI-S– Clinical Global Impressions Severity Scale | A standard measure of symptom severity and treatment response. Collected at baseline, weekly during treatment, posttreatment, and 6 month follow up visit. |
| Center for Magnetic Resonance Research Safety Screen (CMRR) | This assesses subject safety to go in the magnet room and undergo 3T and 7 MRI/MRS. This will be completed at Mayo Clinic and CMRR |
| C-SSRS – Columbia Suicide Severity Rating Scale | This is collected to assess lifetime suicidal ideation and behavior prior to participation, reassessed weekly during 6 week trial of 1 Hz vs 10 Hz rTMS (phase I) and if applicable 2 week extension trial of cTBS or iTBS (phase II) during treatments, posttreatment, and 6 month follow up visit. |
| CTQ – Childhood Trauma Questionnaire | A 28 item self-report scale used to screen for a history of adversity. Collected at baseline. |
| Edinburgh Inventory for Handedness | Used to assess handedness of all Participants. Collected at baseline. |
| Mini International Neuropsychiatric Interview (M.I.N.I) | A structured psychiatric interview (M.I.N.I. for age 18 and M.I.N.I Kid for ages 12-17). Collected at baseline. |
| NIH Toolbox Cognition Battery | 
http://www.healthmeasures.net/explore-measurement-systems/nih-toolbox
 
Cognition measures: http://www.healthmeasures.net/explore-measurement-systems/nih-toolbox/intro-to-nih-toolbox/cognition
 
The NIH Toolbox Cognition Battery, recommended for ages 7+, consists of tests of multiple constructs. It yields individual measure scores and the following summary scores: Education, Handedness, Attention (Flanker Inhibitory Control and Attention Test), Episodic memory (Picture Sequence Memory Test, and Auditory Verbal Learning Test), Executive Function (Dimensional Change Card Sort Test, Flanker Inhibitory Control and Attention Test), Language (Picture Vocabulary Test, Oral Reading Recognition Test), Processing Speed (Pattern Comparison Processing Speed Test), Working Memory (List Sorting Working Memory Test). Collected at baseline, posttreatment, and 6 month follow up.
 |
| PDS – Pubertal Development Scale and Tanner Staging | A self-report questionnaire and line-drawings used to evaluate level of pubertal development. Collected at baseline. |
| Pre/Post Treatment Expectations and Experience Questionnaire (Adolescent and Parent) | Assesses adolescent and parent blinding to treatment arm (1 Hz or 10 Hz) and expectations for treatment outcome. Collected at baseline and posttreatment. |
| SHAPS-Snaith-Hamilton Pleasure Scale | This is a 14 item, self-report measure of validated measure of hedonic capacity. Collected at baseline. |

| Assessment | Description |
|---|--|
| Pediatric Adverse Event Rating Scale | This is a 51 item; self-report measure collected at baseline, weekly during rTMS treatments, posttreatment, and at 6 month follows up visit for adverse event monitoring. |
| Physical Symptoms Checklist | This is a 46 item measure to be collected by the study team (under the supervision of the PI) at baseline, weekly during rTMS treatments, posttreatment, and at 6 month follow up visit for adverse event monitoring. |
| SIT-R3 – Slosson Intelligence Test – Revised | A rapid, validated index of intellectual ability. Its items cover six cognitive domains: Information, Comprehension, Quantitative, Similarities and Differences, Vocabulary, and Auditory Memory. Collected at baseline, if PI the determines there are concerns about cognitive functioning. |
| TASS – Transcranial Magnetic Stimulation Safety Screen | This safety screen is completed prior to TMS for confirmation patient safety. Collected at baseline. |
| UCSD Brief Assessment of Capacity to Consent (UBACC) | This will be given to patients that are 18 years of age who are interested in participating in the MRI/MRS scans at CMRR of age during informed consent. This assesses the patient’s understanding of the MRI/MRS portion of the study. |
| Vital Signs | (Pulse, blood pressure, height, and weight) will be collected at baseline, upon completion of 6 week rTMS (1 Hz or 10 Hz) once again (if applicable) after two week open extension trial (of either cTBS or iTBS), and at 6 month follow up visit. |
| YMRS-Young Mania Rating Scale | This is an 11 item measure used to assess for manic symptoms. The YMRS scale will be completed at baseline and repeated during the course of study participation if symptoms of mania occur in a study participant. If the YMRS is positive, A MINI/MINI-Kid will be repeated to evaluate for mania. If the study participant meets full DSM-5 criteria for mania or hypomania he or she will be discontinued from the study and followed clinically. |
| TMS Neurophysiology Measures (MT, SICI, ICF, LICI, CSP) | Single (motor threshold and cortical silent period) and paired-pulse (intracortical facilitation, short-interval cortical inhibition, long-interval cortical inhibition). TMS neurophysiology measures will be collected in depressed adolescent participants at baseline, weekly during six weeks of rTMS treatment with 1Hz or 10 Hz rTMS (phase I), posttreatment, and weekly for 2 weeks for depressed adolescent participants in a, trial of cTBS or iTBS (phase II). |

Table 3 Phase I Assessments

| Phase I | 1-Week Prestudy | | 6-Week Treatment (1 Hz vs. 10 Hz) | | | | | | 3-Week Post-Treatment Taper | | | 6-Month Follow Up |
|---|---|---------------------------------|-----------------------------------|-------------------|-------------------|-------------------|-------------------|-----------------------------|-----------------------------|-------|-------|-------------------|
| | Wk -2 to -1 ^a (Screening) | Wk 0 ^a (Baseline) | Wk 1 ^b | Wk 2 ^b | Wk 3 ^b | Wk 4 ^b | Wk 5 ^b | Wk 6 ^{b,c} /E T | Wk 1 | Wk 2 | Wk 3 | |
| | -7 ^a | 0 ^a | 1-5 | 8-12 | 15-19 | 22-26 | 29-35 | 36-42 | 43-49 | 50-56 | 57-63 | |
| Informed Consent/Assent/HIPAA | X | | | | | | | | | | | |
| CMRR Safety Screen (prior to MRI/MRS) | X | | | | | | | X | | | | |
| UCSD Brief Assessment of Capacity to Consent (UBACC) (only patients age 18 participating in MRI/MRS scans at CMRR) | X | | | | | | | | | | | |
| MRI/MRS Study(Before Baseline Appt.) | X | | | | | | | X | | | | |
| Transcranial Magnetic Stimulation Adult Safety Screen (TASS) | X | | | | | | | | | | | |
| Antidepressant Treatment History Form (ATHF) | X | | | | | | | | | | | |
| Abnormal Involuntary Movement Scale (AIMS) | X | | X | X | X | X | X | X | X | X | X | X |
| MINI / MINI-Kids | X | | | | | | | | | | | |
| CTQ | | X | | | | | | | | | | |
| PDS | | X | | | | | | | | | | |

| Phase I | 1-Week Prestudy | | 6-Week Treatment (1 Hz vs. 10 Hz) | | | | | | 3-Week Post- Treatment Taper | | | 6- Mont h Follo w Up |
|--------------------------------------|---|---------------------------------|--------------------------------------|----------------------|----------------------|----------------------|----------------------|--------------------------------|---------------------------------------|----------------|----------------|----------------------------------|
| | Wk -2 to - 1 ^a (Screening) | Wk 0 ^a (Baseline) | Wk 1 ^b | Wk 2 ^b | Wk 3 ^b | Wk 4 ^b | Wk 5 ^b | Wk 6 ^{b,c} /E T | Wk 1 | Wk 2 | Wk 3 | |
| | -7 ^a | 0 ^a | 1-5 | 8- 12 | 15- 19 | 22- 26 | 29- 35 | 36-42 | 43- 49 | 50- 56 | 57 - 63 | |
| SHAPS | | X | | | | | | | | | | |
| Pre/Post-TEEQ-P | | X | | | | | | X | | | | |
| Pre/Post-TEEQ-A | | X | | | | | | X | | | | |
| Efficacy Assessments | | | | | | | | | | | | |
| BDI-II | X | X | | | | X | | X ^{c,d} | X | | X ^d | |
| CDRS-R | X | X | X | X | X | X ^d | X | X ^{c,d} | X | X | X ^d | X |
| CGI-S | X | X | | | | X | | X ^{c,d} | X | | X ^d | X |
| Neuropsychological Assessments | | | | | | | | | | | | |
| NIH Toolbox | | X | | | | | | X ^{c,d} | | | | X |
| SIT-R3 | | X | | | | | | | | | | |
| YMRS ^d | | X | | | | | | | | | | |
| C-SSRS | X | X | X ^d | X ^d | X ^d | X ^d | X ^d | X ^{c,d} | X ^d | X ^d | X ^d | X |
| Safety Assessments | | | | | | | | | | | | |
| Physical examination | X | | | | | | | | | | | |
| Vital Signs | X | | | | | | | X ^c | X | | | |
| Urine drug screen | X | | | | | | | | | | | |
| Pregnancy test ^e | X | | | | | | | | | | | |
| Audiometry assessment | | X | | | | | | X ^c | | | | X |
| Physical Symptom Checklist | | X | X | X | X | X | X | X | | | | X |
| Pediatric Adverse Event Rating Scale | | X | X | X | X | X | X | X | | | | X |
| Adverse Events | X-----X | | | | | | | | | | | |
| Prior/Concomitant Treatment | X-----X | | | | | | | | | | | |

| Phase I | 1-Week Prestudy | | 6-Week Treatment (1 Hz vs. 10 Hz) | | | | | | 3-Week Post-Treatment Taper | | | 6-Month Follow Up |
|--|---|---------------------------------|-----------------------------------|------------------------|------------------------|------------------------|------------------------|-----------------------------|-----------------------------|-------|-------|-------------------|
| | Wk -2 to -1 ^a (Screening) | Wk 0 ^a (Baseline) | Wk 1 ^b | Wk 2 ^b | Wk 3 ^b | Wk 4 ^b | Wk 5 ^b | Wk 6 ^{b,c} /E T | Wk 1 | Wk 2 | Wk 3 | |
| | -7 ^a | 0 ^a | 1-5 | 8-12 | 15-19 | 22-26 | 29-35 | 36-42 | 43-49 | 50-56 | 57-63 | |
| Motor Threshold Determination^g | | X | | | | | | | | | | |
| TMS Treatment Session (daily × 5 weekdays/week) | | | X-- -X ^b | X-- -X ^b | X-- -X ^b | X-- -X ^b | X-- -X ^b | X-- -X ^b | | | | |
| TMS neurophysiology measures (MT, SICI, ICF, LICI, CSP) | | X | X | X | X | X | X | X | | | | |
| Post-Treatment Taper TMS Session(s) (3X/Wk 1, 2X/Wk 2, 1X/Wk 3) | | | | | | | | | X | X | X | |

- A maximum of 7 days may elapse between the screening and baseline visits; a maximum of 5 days may elapse between the baseline visit and the first treatment day of Week 1. All baseline assessments must be completed before 1st TMS treatment.
- The first visit during each week of treatment should occur on a Monday, with daily treatment sessions occurring on Monday through Friday of each week.
- Participants who prematurely discontinue should complete all Week 6 procedures within 2 days after their last TMS treatment session.
- Efficacy and neuropsychological assessments to be performed after last TMS treatment session on last day of the treatment week when assessments are required. YMRS to be completed if symptom indicating mania occurs. If positive, a MINI/MINI-Kid must be repeated to determine if Participant meets full DSM-5 criteria for mania or hypomania. If positive, participant to be discontinued from the study and followed clinically.
- If Participant is female of childbearing potential, a urine pregnancy test will be performed at screening. Note that parents or guardians will not be told the results of the pregnancy test without the participant's permission. But if the participant's doctor believes that being pregnant may cause serious health problems, they may need to tell the parent/guardian the pregnancy test results.
- Adverse events occurring prior to randomization will be recorded as part of each patient's medical history. Those AEs occurring following the first TMS treatment session through 30 days after last TMS treatment session will be collected.
- In addition to the indicated day, Motor Threshold Determination (MT) may be repeated at any time during the course of the active TMS treatment sessions based on clinical assessment of the supervising physician.
Medication treatment for emergent insomnia and emergent anxiety is permitted (refer to protocol for usage allowance). Refer to Appendix A for the Concomitant Medication List.
- The following assessments will be completed once only for healthy controls at the Mayo Clinic site: Urine testing (drugs and pregnancy if female), vitals (blood pressure, pulse, height and weight), GUID (demographics) form, physical examination record, Transcranial Magnetic Stimulation Adult Safety Screen, M.I.N.I. Kid, Children's Depression Rating Scale, Columbia - Suicide Severity Rating Scale, Childhood Trauma Questionnaire, Clinical Global Impressions, Center for Magnetic Resonance Research Screening Form, Edinburgh Handedness Inventory, Scale for Pubertal Development, Beck Depression Inventory-II, Authorization to Release Information (if applicable)

Table 4 Phase II Assessments

| Week | Week 1 | Week 2 | 6 Month Follow-up |
|---|--------|--------|-------------------|
| Days | 1-5 | 8-12 | |
| Informed Consent/Assent | X | | |
| Motor Threshold | X | | |
| CDRS-R | X | X | X |
| CGI | X | X | X |
| C-SSRS | X | X | X |
| TMS neurophysiology measures (MT, SIC1, ICF, LIC1, CSP) | X | X | |
| AIMS | X | X | X |
| Vital Signs | X | X | |
| Physical Symptom Checklist | X | X | X |
| Pediatric Adverse Event Rating Scale | X | X | X |
| Audiometry assessment | | X | X |
| NIH toolbox | | X | X |
| Adverse Events ^f | Daily | Daily | |
| Prior/Concomitant Treatment | Daily | Daily | |

Every treatment day of Phase II treatment a pre-treatment checklist will be completed by 2 members of study staff prior to initiating treatment to ensure treatments are performed properly and accurately. The 2nd member of study staff may assist telephonically if necessary.

7 Statistical Plan

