been reported to result from single-pulse TMS but have occurred most frequently with repetitive rTMS.^{74,75} The risk for seizure with iTBS may be higher than standard rTMS (1 Hz or 10 Hz).⁷⁴ Participants who have a past history of neurological disorders such as strokes or epilepsy have the greatest risk. This incidence is still low (0.6% or less) which is comparable to the reported incidence of seizures with antidepressant medications.^{74,75} The role of TMS in some case reports of seizures is equivocal^{76,77} but the possibility of TMS inducing seizures in participants without prior neurological pathology cannot be entirely discounted. There have been 17 case reports of seizures during TMS in healthy participants, depressed participants, or participants with other disorders not thought to confer a seizure risk (such as pain).⁷² It is also noteworthy, that in a recent, multicenter trial of rTMS involving 301 adult patients receiving rTMS at 120% motor threshold, 3,000 pulses per session, five days a week for 4-6 weeks (this is rTMS delivered at the upper limits of recommended safety guidelines) there were no seizures nor elevated rates of serious adverse events.³⁸ Reported seizures associated with rTMS have also been self-limited and beyond careful monitoring and neurological assessment have not required acute treatment. It is also important to note that there is no evidence that a single seizure, or even a series of induced seizures, makes a subsequent seizure more likely in an otherwise healthy individual. However, it is also true that there are potential psychosocial consequences of a seizure, including the potential psychosocial impact. There are 3 case reports of seizures in adolescents with depression undergoing rTMS treatments. In two of these instances the adolescents were taking psychotropic medications.^{78,79} In one instance the adolescent used alcohol the night before rTMS treatment.⁷⁹ One case report described a seizure in an adolescent undergoing deep TMS.⁸⁰ In our experience thus far and to our knowledge there have been no seizures in depressed adolescents receiving NeuroStar rTMS treatments.

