8.1 Definitions

Unanticipated Adverse Device Effect (UADE)

A UADE is any serious adverse effect on health or safety or any life-threatening problem or death caused by, or associated with, a device if that effect, problem or death was not previously identified in nature, severity, or degree of incidence in the investigational plan or IDE application (including a supplementary plan or application), or any other unanticipated serious problem associated with a device that relates to the rights, safety, or welfare of participants.

Adverse Effect (Event)

Any untoward medical occurrence in a participant involved in clinical study of an investigational device; regardless of the causal relationship of the problem with the device or, if applicable, other study related treatment(s).

Associated with the investigational device: there is a reasonable possibility that the adverse effect may have been caused by the investigational device.

Life-threatening adverse effect: Any adverse effect that places the participant, in the view of either the investigator or the sponsor, at immediate risk of death from the effect **as it occurred**. It does not include a reaction that, had it occurred in a more severe form, might have caused death.

Serious adverse effect: An adverse effect is considered “serious” if, in the view of either the investigator or the sponsor, it results in any of the following outcomes:

- death
- a life-threatening AE
- inpatient hospitalization or prolongation of existing hospitalization
- a persistent or significant disability/incapacity
- a congenital anomaly/birth defect.

Unanticipated adverse effect: Any adverse effect, the nature, specificity, severity, or frequency of which is not consistent with the risk information in the clinical study protocol or elsewhere in the current IDE application.

General Physical Examination Findings

At screening, any clinically significant abnormality should be recorded as a preexisting condition. At the end of the study, any new clinically significant findings/abnormalities that meet the definition of an adverse event must also be recorded and documented as an adverse event.

Hospitalization, Prolonged Hospitalization or Surgery

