- **Serious:** Serious problems or events that results in significant harm, (which may be physical, psychological, financial, social, economic, or legal) or increased risk for the Participant or others (including individuals who are not research Participants). These include: (1) death; (2) life threatening adverse experience; (3) hospitalization - inpatient, new, or prolonged; (4) disability/incapacity - persistent or significant; (5) birth defect/anomaly; (6) breach of confidentiality and (7) other problems, events, or new information (i.e. publications, DSMB reports, interim findings, product labeling change) that in the opinion of the local investigator may adversely affect the rights, safety, or welfare of the Participants or others, or substantially compromise the research data, **AND**
- **Unanticipated:** (i.e. unexpected) problems or events are those that are not already described as potential risks in the protocol, consent document, not listed in the Investigator's Brochure, or not part of an underlying disease. A problem or event is "unanticipated" when it was unforeseeable at the time of its occurrence. A problem or event is "unanticipated" when it occurs at an increased frequency or at an increased severity than expected, **AND**
- **Related:** A problem or event is "related" if it is possibly related to the research procedures.

An *adverse event* is any untoward, undesired, or unplanned event in the form of signs, symptoms, disease, or laboratory or physiological observations occurring in a person who has received NeuroStar TMS therapy (1 Hz, 10 Hz, cTBS, or iTBS). The event need not be causally related to the NeuroStar device or the present clinical trial. An AE includes, but is not limited to:

- Any clinically significant worsening of a pre-existing condition;
- An AE occurring from overdose (i.e., a dose higher than that described in the protocol) of a NeuroStar TMS device, whether accidental or intentional;
- An AE occurring from abuse (e.g., use for non-clinical reasons) of a NeuroStar TMS device;
- An AE that has been associated with the discontinuation of the use of a NeuroStar TMS device; a *preexisting condition* is a clinical condition (including a condition being treated)

that is diagnosed before an informed consent form is signed and is documented as part of the Participant's medical history.

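### The protocol contradicts itself on when adverse event collection starts and whom it covers, so harm after consent but before treatment may be left out of the safety endpoint

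*Combined protocol and SAP*

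**What the plan says.** Two pieces of text are narrow.

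- Table 3 footnotes: "Adverse events occurring prior to randomization will be recorded as part of each" patient's medical history. The next sentence reads: "Those AEs occurring following the first TMS treatment session through 30 days after last TMS treatment session will be collected". The AE row of Table 4 (Phase II) carries footnote letter f, which matches this note's place in the Table 3 list.
- Section 8.1, second AE definition (after the UPIRTSO criteria): an AE is an event "occurring in a person who has received NeuroStar TMS therapy (1 Hz, 10 Hz, cTBS, or iTBS".

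Other current text is broad.

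- Section 8.1, first AE definition: "Any untoward medical occurrence in a participant involved in clinical study of an investigational device; regardless of the causal relationship" to the device or other study treatment. It has no start time and does not require that treatment has begun.
- Section 8.2 puts every AE during the study on the case report form. Section 8.3 records, at each required visit, all AEs since the previous one. Section 3.4 (Table 1, primary safety endpoints) and Table 2 evaluate AEs at every visit.
- Section 8.1 describes a preexisting condition as one diagnosed before the consent form is signed, and it is these conditions that go into medical history.

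Section 1.5.2 names the relevant risk: seizures have "been reported to result from single-pulse TMS but have occurred most frequently with repetitive rTMS".

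**The concern.** Several study procedures take place after consent and before the footnote's window opens. They are the single- and paired-pulse testing that sets the ICF stratum (sections 4.3 and 6.2), motor threshold determination at baseline (Table 3; done per the NeuroStar manual under section 5.3), and, for those who accept it, the first 3 T and 7 T scans (sections 3.1 and 6.1). Some participants will also recently have stopped antidepressants (section 4.1).

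If staff follow the footnote, a syncope during baseline ICF testing is filed as background history. If they follow section 8.2, the same event is an AE. AEs are a primary safety endpoint, and section 8.5 contains a study-level rule triggered by a second serious adverse event. Neither should depend on which paragraph the person completing the form has read. The participants are adolescents, mostly minors by the age range of 12 to 18, and the healthy controls have no prospect of treatment benefit.

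**Working it through.** The plan gives no figure to reproduce. The check sets the texts side by side and counts days from the stated windows.

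**Inputs**

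- Screening to baseline: at most 7 days (Table 3 footnotes). Consent is taken at screening (section 6.1).
- Baseline to first treatment day: at most 5 days (Table 3 footnotes). Randomisation is at the baseline visit (section 6.2).
- Washout: at least 1 week before baseline, or 4 weeks for fluoxetine (section 4.1).
- Planned numbers: 120 in Phase I, up to 100 depressed participants scanned, 30 healthy controls scanned once (Study Summary, section 3.1).

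**Step 1: the uncovered period.** Screening to first treatment is at most 7 + 5 = 12 days. In the first 7, the footnote files events as medical history. In the last 5, after randomisation, events are not medical history and are not yet collected, so neither sentence assigns them.

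**Step 2: the part of washout that matters.** For fluoxetine, 28 − 7 = 21, so at least 21 days of the required washout fall before consent and would not be trial AEs under any of these rules. For other antidepressants, 7 − 7 = 0, so the minimum washout can lie wholly after consent. Only the post-consent part belongs to this point.

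**Step 3: the two sets of rules applied to the same events.**

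| Event | Footnote and second 8.1 definition | First 8.1 definition, 8.2, 8.3 |
|---|---|---|
| Syncope in baseline TMS testing | Medical history; not an AE | AE |
| Harm at first 7 T scan | Medical history; not an AE | AE |
| Event after randomisation, before first session | Unassigned by the footnote; not an AE by definition | AE |
| Harm at a healthy control's scan | No treatment session, so collection never opens; not an AE | AE, if controls are participants |
| Syncope in weekly TMS testing | Collected | AE |

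The rules disagree on the first four rows and agree on the last. For controls there is a further gap: the list of their assessments under Table 3 contains no AE item.

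**Step 4: exposure.** The first four rows correspond to about 120 baseline testing sessions, up to 100 first scans, the interval before first treatment in about 120 people, and 30 control scans. These are opportunities for an event, not expected events. The documents give no rate from which to project a count.

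**Step 5: stopping rules in section 8.5.** The seizure rule states no time window. The suicide rule is limited to treatment weeks. The serious adverse event rule states no window, but it depends on what counts as an adverse event, and that is where the two definitions part. A serious event between consent and first treatment counts under one and not under the other.

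**The case against.** The strongest reply is that the broad text governs and nothing serious is lost. Much of this stands. Sections 1.5.2 and 5.3 send any seizure to the IRB, DSMB, manufacturer and FDA. Section 4.4.1 withdraws anyone who has one. Serious unanticipated problems are reportable if possibly related to research procedures, not only to NeuroStar sessions (sections 8.1 and 8.3.1). Section 8.1 treats doubtful cases as serious. The C-SSRS is given at screening and baseline, and the symptom scales at baseline.

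A reader might therefore go too far in three ways:

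- One might infer that pre-treatment harm never counts as a trial AE. The first definition in 8.1 and sections 3.4, 8.2 and 8.3 say otherwise.
- One might infer that a seizure in baseline testing is not counted toward the two-participant seizure rule. Nothing in section 8.5 excludes it.
- One might infer that all TMS testing, both scans and the whole washout are affected. Weekly testing falls inside the footnote's window, the second scan at least partly does, and at least 21 days of fluoxetine washout precede consent. Twelve days is also a maximum, since baseline procedures may be done on the screening day.

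It can also be said that the narrow window is deliberate, because section 1.2 disclaims any intention to collect safety data on the Magstim device used for ICF testing. That does not explain the gap. Events from the same device are collected once treatment has begun, and the disclaimer does not cover the scan, the washout or motor threshold testing. Nor does opposing text elsewhere cure the footnote: it is a stated rule, and it is repeated for Phase II.

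**Conclusion.** The contradiction is real and of moderate severity. Under the footnote and the second definition, three kinds of event may be left out of the AE endpoint: post-consent harm before randomisation, events in the up to 5 days before first treatment, and any event in the 30 controls. Whether a serious pre-treatment event counts toward the serious adverse event rule in section 8.5 depends on the definition used.

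The comparison of 1 Hz with 10 Hz is not biased by events before randomisation, because they cannot depend on the assigned arm. The primary analysis is untouched. What is at risk is the completeness of the safety record for study procedures.

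This rests on consent at screening and randomisation at the baseline visit, as sections 6.1 and 6.2 describe. The AE row in Table 3 appears to run from screening, but the extracted layout is too unreliable to lean on. What the DSMB would be shown cannot be judged, because its charter is not part of the documents.

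**What to change.** 1. Amend the Table 3 footnote and the second AE definition in section 8.1 to agree with the first definition and section 8.2. AE and serious AE collection then starts at the first study procedure after consent, for all participants. Say explicitly that healthy controls are included, and add an AE item to their assessment list.
2. Keep treatment-emergent events, already defined in section 8.1, as the subset used for arm comparisons. Wider collection then does not dilute the contrast.
3. Use signature of consent as the single cut-off for a preexisting condition. Section 8.1 also refers to the start of the study, and the footnote uses randomisation.
4. Reconcile section 8.5 with the single definition, so that it is clear which pre-treatment events its rules count. Which events should stop the study is for the sponsor and DSMB to settle.

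The cost is amendment wording and a few extra AE entries per participant. Reported AE counts will be slightly higher, and reporting treatment-emergent events separately keeps that easy to interpret.
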